**Table 5-5 Statistical analysis to address the secondary objectives**

SI No.	Endpoints	Landmark visits	Endpoint type	Imputation approach and Statistical model	Analysis set	Sensitivity analyses
Secondary Endpoint						
1	Change from baseline in BMI SDS (%)	Week 16, Week 52	Continuous	J2R-MI ANCOVA	FAS	NA
2	Change from baseline in BMI (Kg/m  )	Week 16, Week 52	Continuous	J2R-MI ANCOVA	FAS	NA
3	Change from baseline in BMI (%)	Week 16, Week 52	Continuous	J2R-MI ANCOVA	FAS	NA
4	Percentage of Subjects achieving $\geq 5\%$ reduction in baseline BMI	Week 16, Week 52	Categorical	J2R-MI Logistic Regression	FAS	NA
5	Percentage of subjects with no increase in BMI SDS	Week 16, Week 52	Categorical	J2R-MI Logistic Regression	FAS	NA

SI No.	Endpoints	Landmark visits	Endpoint type	Imputation approach and Statistical model	Analysis set	Sensitivity analyses
6	Change from baseline in hyperphagia score (hyperphagia total score, hyperphagic behaviour, drive and severity score)	Week 16, Week 52	Continuous	J2R-MI ANCOVA	FAS	NA
7	Change from baseline in Glycaemic category	Week 16, Week 52	Categorical	J2R-MI Logistic Regression	FAS	NA
8	Change from baseline in Body weight (kg, lb and %)	Week 16, Week 52	Continuous	J2R-MI ANCOVA	FAS	NA
9	Change from baseline in Waist circumference (cm)	Week 16, Week 52	Continuous	J2R-MI ANCOVA	FAS	NA
10	Change from baseline in Waist-to-hip circumference ratio (ratio)	Week 16, Week 52	Continuous	J2R-MI ANCOVA	FAS	NA
11	Change from baseline in Cardiovascular biomarker (hsCRP) (mg/L)	Week 16, Week 52	Continuous	J2R-MI ANCOVA (with log transformed response and baseline values)	FAS	NA
12	Change from baseline in TC (mmol/L )	Week 16, Week 52	Continuous	J2R-MI ANCOVA (with log transformed response and baseline values)	FAS	NA

SI No.	Endpoints	Landmark visits	Endpoint type	Imputation approach and Statistical model	Analysis set	Sensitivity analyses
13	Change from baseline in LDL-cholesterol (mmol/L )	Week 16, Week 52	Continuous	J2R-MI ANCOVA (with log transformed response and baseline values)	FAS	NA
14	Change from baseline in HDL-cholesterol (mmol/L )	Week 16, Week 52	Continuous	J2R-MI ANCOVA (with log transformed response and baseline values)	FAS	NA
15	Change from baseline in non-HDL cholesterol (mmol/L)	Week 16, Week 52	Continuous	J2R-MI ANCOVA (with log transformed response and baseline values)	FAS	NA
16	Change from baseline in VLDL (mmol/L)	Week 16, Week 52	Continuous	J2R-MI ANCOVA (with log transformed response and baseline values)	FAS	NA
17	Change from baseline in TG (mmol/L)	Week 16, Week 52	Continuous	J2R-MI ANCOVA (with log transformed response and baseline values)	FAS	NA
18	Change from baseline in FFA (mmol/L)	Week 16, Week 52	Continuous	J2R-MI ANCOVA (with log transformed response and baseline values)	FAS	NA
19	Change from baseline in Systolic Blood Pressure (mmHg)	Week 16, Week 52	Continuous	J2R-MI ANCOVA	FAS	NA
20	Change from baseline in Diastolic Blood Pressure (mmHg)	Week 16, Week 52	Continuous	J2R-MI ANCOVA	FAS	NA
21	Change from baseline in HbA 1c (%)	Week 16, Week 52	Continuous	J2R-MI ANCOVA	FAS	NA

SI No.	Endpoints	Landmark visits	Endpoint type	Imputation approach and Statistical model	Analysis set	Sensitivity analyses
22	Change from baseline in FPG (mmol/L)	Week 16, Week 52	Continuous	J2R-MI ANCOVA	FAS	NA
23	Change from baseline in fasting insulin (pmol/L)	Week 16, Week 52	Continuous	J2R-MI ANCOVA (with log transformed response and baseline values)	FAS	NA
24	Change from baseline in C-peptide (nmol/L)	Week 16, Week 52	Continuous	J2R-MI ANCOVA (with log transformed response and baseline values)	FAS	NA
25	Change from baseline in HOMA-B	Week 16, Week 52	Continuous	J2R-MI ANCOVA (with log transformed response and baseline values)	FAS	NA
26	Change from baseline in HOMA-IR	Week 16, Week 52	Continuous	J2R-MI ANCOVA (with log transformed response and baseline values)	FAS	NA
27	Change from baseline in Pulse (beats/min)	Week 16, Week 52	Continuous	J2R-MI ANCOVA	SAS	NA
28	Relative change from baseline in Amylase	Week 16, Week 52	Continuous	MMRM (with log transformed response and baseline values)	SAS	NA
29	Relative change from baseline in Lipase	Week 16, Week 52	Continuous	MMRM (with log transformed response and baseline values)	SAS	NA

#### 5.4.1.2 Supportive secondary PK endpoint

Model-derived area under the curve (AUC) over the dosing interval in steady state.

#### 5.4.1.3 Supportive secondary safety endpoints

##### Adverse events

AEs will be summarised by System organ class (SOC) and Preferred term (PT) level for the safety analysis set separately for two periods:

- In trial: defined as events with onset date on or after the first day of trial product administration and no later than the last study visit.
- On treatment: defined as events with onset date on or after the first day of trial product administration and no later than whatever comes first: a) 14 days after the last day on trial product, b) FU visit (subjects with trial product discontinued), or c) last study visit (early withdrawn subjects without FU visit).
- A treatment emergent adverse event (TEAE) is defined as an event that occurs in the ‘on treatment’ period.

In addition, the TEAEs will be summarised for the double blinded (0-16 week) and open label (end of week 16 to week 52).

The AEs will be coded using the most recent version of the Medical Dictionary for regulatory Activities (MedDRA). They will be presented in terms of the number and percentage of subjects with at least one event, the number of events and the event rate per 1000 years. AEs in the screening period will be presented in listings.

### **Hypoglycaemic episodes**

The hypoglycaemic episodes will be summarised descriptively by severity and treatment in terms of the number and percentage of subjects with at least one event and the total number of events. In the same way as for AEs, there will be separate summaries for the “in trial” and “on treatment” periods. Hypoglycaemic episodes in the screening period will be presented in listings.

Hypoglycaemic episodes will also be summarised based on newer classification recommended by International Hypoglycaemia Study Group (IHSG) 2017, ADA 2018 and ISPAD 2018 for clinically significant hypoglycaemia (PG confirmed <3.0 mmol/L) (see Appendix 3 for the new classification)

The hypoglycaemic episodes will be summarised for the double blinded period (0-16 week) and open label period (end of week 16 to week 52).

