#### 4.2.2.3 Supportive secondary safety endpoints

- Number of treatment-emergent adverse events during the trial
- Number of severe treatment emergent episodes of hypoglycaemia
- Number of blood glucose confirmed symptomatic episodes of hypoglycaemia
- Occurrence of anti-liraglutide antibodies

Change from baseline to 16 and 52 weeks in:

- Electrocardiogram (ECG)
- Pulse
- Laboratory parameters:
  - Haematology: haemoglobin, haematocrit, thrombocytes, erythrocytes, leukocytes, differential count (eosinophils, neutrophils, basophils, lymphocytes, monocytes)
  - Biochemistry: creatinine, creatine kinase (CPK), urea, albumin, bilirubin (total), alanine aminotransferase (ALT), aspartate aminotransferase (AST), alkaline phosphatase, sodium, potassium, calcium total, calcium albumin corrected, amylase, lipase, and carcinoembryonic antigen (CEA)
  - Hormone levels including: calcitonin, insulin-like growth factor-1 (IGF-1), thyroid stimulating hormone (TSH), free thyroxine (free T4), prolactin, adrenocorticotrophic

Protocol: Liraglutide  
Trial ID: NN8022-4179  
UTN: U1111-1162-7884  
EudraCT no.: 2014-004415-37

~~CONFIDENTIAL~~

Date:	16 July 2020	Novo Nordisk
Version:	5.0	
Status:	Final	
Page:	27 of 125	

hormone (ACTH), cortisol, dehydroepiandrosterone sulfate (DHEAS), luteinising hormone (LH), follicle stimulating hormone (FSH), estradiol (females), testosterone (males)

- Pubertal status
- Physical examination including height
- Part A only: Mental health assessed by Columbia Suicidality Severity Rating Scale (C-SSRS) and Patient Reported Health Questionnaire-9 (PHQ-9)

\*Key supportive secondary endpoint prospectively selected for posting on clinicaltrials.gov and EudraCT)

Protocol: Liraglutide  
 Trial ID: NN8022-4179  
 UTN: U1111-1162-7884  
 EudraCT no.: 2014-004415-37

[figure not shown]
CONFIDENTIAL

Date: 16 July 2020  
 Version: 5.0  
 Status: Final  
 Page: 28 of 125  
 Novo Nordisk

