### Classification of Hypoglycaemia:

Treatment emergent: Hypoglycaemic episodes will be defined as treatment emergent if the onset of the episode occurs on or after the first day of trial product administration, and no later than 14 days after the last day on trial product.

Nocturnal hypoglycaemic episodes: Are episodes occurring between 00:01 and 05.59 both inclusive.

Hypoglycaemic episodes are classified according to the Novo Nordisk classification of hypoglycaemia and the American Diabetes Association (ADA) classification of hypoglycaemia (see [Figure 17-1](#)).

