**Table 4-2 Overview of defined analysis set**

Defined Analysis Data Sets	Description
In-trial	
The time period where the subject is supposed to be in the trial. The in-trial period begins at date of first dose of trial product and ends at the date of:
 
 
• The last direct subject-site contact, which is planned to take place at a follow-up visit
 
• Withdrawal date for subjects who withdraw informed consent
 
• The last subject-investigator/site contact as defined by investigator for subjects who are lost to follow up
 
• Date of death for subjects who die before any of the above
 

On-treatment
	
The time period where subjects are treated with trial product. The on-treatment period begins on the date of first dose of trial product and at the earliest date of:
 
 
• The follow-up visits (subjects with trial product discontinued)
 
• Last day on trial product + 14 days
 
• Last study visit (early withdrawn subjects without FU visit).
 
 
On-treatment period is defined for Liraglutide 3.0 mg as week 0-52 and for Placebo week 0-16.

Double blinded
	
The double blind period is from first dose of trial product to week 16 (0-16).
 
For the events occurring in double blinded period (AE and Hypoglycaemic episode)
 
 
• For liraglutide double blinded period will be from (week 0) to (week 16)
 
• For placebo double blinded period will be from (week 0) to (week 16 + 14 days)
 

Open label
	
The open label period is of duration 36 weeks that is from end of week 16 to week 52.
 
For the events occurring in open label period (AE and Hypoglycaemic episode)
 
 
• For Liraglutide open label period will be from (end of week 16) to (52 weeks + 14 days)
 
• For placebo open label period will be from (end of week 16 +14 days ) to (week 52)
 

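### The on-treatment hypoglycaemia tables give counts and percentages but no exposure-based rate, although the on-treatment window is about three times longer on liraglutide than on placebo

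*SAP*

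**What the plan says.** **Metrics.** SAP 5.4.1.3 (Hypoglycaemic episodes) and Protocol 17.4.1.2 summarise episodes descriptively, by severity and treatment, "in terms of the number and percentage of subjects with at least one event and the total number of events". No rate is mentioned. For adverse events, SAP 5.4.1.3 and Protocol 17.4.1.2 also require "the number of events and the event rate per 1000 years".

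**Periods.** The SAP plans hypoglycaemia summaries for the in-trial and on-treatment periods, and for the double-blind and open-label periods. The sentence beginning "In the same way as for AEs, there will be separate summaries for the" carries over the adverse-event periods, not the adverse-event metrics.

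**Windows.** SAP Table 4-2: "On-treatment period is defined for Liraglutide 3.0 mg as week 0-52 and for Placebo week 0-16". Protocol 17.4.1.2 counts an episode as treatment emergent if it starts "no later than 14 days after the last day on trial product", which adds two weeks in both arms.

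**Endpoints.** Protocol 4.2.2.3 lists "Number of severe treatment emergent episodes of hypoglycaemia" and, separately, blood-glucose-confirmed symptomatic episodes, the latter without the treatment-emergent restriction. SAP 6.3.1.5 applies the new level 1-3 classification to treatment-emergent episodes.

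**The concern.** Placebo injections stop at week 16, so a treatment-emergent episode can be seen for far longer on liraglutide than on placebo. A table with subjects as its only denominator mixes risk with observation time. For adverse events the rate deals with this; for hypoglycaemia nothing in the SAP does.

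The on-treatment table is the natural source for the severe-episode endpoint, because that endpoint is defined as treatment emergent. A reader comparing its two columns could see an excess on liraglutide that comes only from longer follow-up. Comparing safety between arms is a stated secondary objective, and the SAP does not say which hypoglycaemia table serves it.

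**Working it through.** **The plan's own figure.** The documents give no expected hypoglycaemia rate. The only plan figures used here are the arm sizes in Protocol Table 17-2, 38 and 19, total 57. That total reproduces: corrected difference 0.9 × 0.23 = 0.207; corrected SD √(0.25² + (2/3)(0.1)(0.9)(0.23²)) = 0.256; two-sided 5%, 80% power and 2:1 allocation give 57.

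**Step 1: window ratio, liraglutide to placebo**

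| Reading | Weeks | Ratio |
|---|---|---|
| With 14-day tail (Protocol 17.4.1.2) | 54 v 18 | 3.00 |
| Nominal (SAP Table 4-2) | 52 v 16 | 3.25 |
| eCRF recording ends at V18, week 48 (Protocol 8.5.2) | 48 v 18 | 2.67 |
| With tail and the protocol's 10% and 20% withdrawal, assumed linear | 47.8 v 17.2 | 2.78 |

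The last row is 16 × 0.95 + 36 × 0.85 + 2 = 47.8 and 16 × 0.95 + 2 = 17.2. The flow chart appears to schedule episode collection at V19 as well; stopping there would give 52/18 = 2.89, inside the range.

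**Step 2: on-treatment table at equal risk.** Assume the same constant rate λ per year in both arms, with t = weeks/52.18. Expected episodes = n × λ × t; proportion affected = 1 − exp(−λt). The range of λ is an assumption. With 54 v 18 weeks:

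| λ per year | Episodes | % affected | Ratio of % |
|---|---|---|---|
| 0.1 | 3.9 v 0.7 | 9.8 v 3.4 | 2.9 |
| 0.5 | 19.7 v 3.3 | 40.4 v 15.8 | 2.55 |
| 1 | 39.3 v 6.6 | 64.5 v 29.2 | 2.2 |
| 2 | 78.7 v 13.1 | 87.4 v 49.8 | 1.75 |

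Over the same λ, the ratio of percentages is 3.14 down to 1.88 with 52 v 16 weeks, and 2.59 down to 1.69 with 48 v 18 weeks. Episodes per subject differ by the window ratio itself, about 3.

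**Step 3: the other planned summaries at equal risk**

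| Summary | Weeks | Window ratio | % affected at λ = 0.5 |
|---|---|---|---|
| Double-blind | 16 v 18 | 0.89 | 14.2 v 15.8 |
| Open-label | 38 v 34 | 1.12 | 30.5 v 27.8 |
| In-trial | about 54 v 54 | 1.0 | 40.4 v 40.4 |

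The double-blind windows differ because Table 4-2 says "For liraglutide double blinded period will be from (week 0) to (week 16") but adds 14 days for placebo. The tilt is small and in the opposite direction.

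**Step 4: with a rate.** Exposure is 38 × 54/52.18 = 39.3 years and 19 × 18/52.18 = 6.6 years. At λ = 0.5, the 19.7 and 3.3 expected episodes both give 500 per 1000 years, a ratio of 1.0.

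**The case against.** The strongest reply is that the SAP already plans three summaries with near-equal windows. The safety objective is worded as placebo at 16 weeks and no treatment at 52 weeks, which corresponds to the double-blind and in-trial summaries. Hypoglycaemia is descriptive, no test rests on it, and Table 4-2 states the arm windows openly. Any distortion exaggerates risk on liraglutide rather than hiding it. Table layouts are left to the programming specification and mock tables, which were not available and may contain a rate.

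Much of this stands, and it rules out three stronger readings that a reader might infer:

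- **That all hypoglycaemia reporting is distorted.** It is not: Step 3 gives ratios close to 1 outside the on-treatment tables.
- **That liraglutide shows a sixfold excess at equal risk.** Raw totals would be about 6:1, but a factor of 2 is the 2:1 allocation, visible from the arm sizes. Only the factor of about 3 comes from time.
- **That both hypoglycaemia endpoints are affected by definition.** Only the severe one is labelled treatment emergent.

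What remains is that the other summaries do not repair the on-treatment tables. The SAP neither names the between-arm comparison nor warns against comparing those columns, and it already requires the rate for adverse events.

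**Conclusion.** The point holds for the on-treatment hypoglycaemia tables, including those by the new classification. They lack a rate while the liraglutide window is 2.7 to 3.25 times as long as the placebo window. At equal underlying risk and 54 v 18 weeks, episodes per subject would be 3 times higher on liraglutide and the percentage affected about 1.75 to 2.9 times higher.

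The percentages rest on a constant, equal rate in both arms, assumed between 2 and 0.1 per year because the documents give none. The window ratio does not depend on that assumption. This is a reporting gap in a descriptive safety summary; no primary conclusion is affected.

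**What to change.** In SAP 5.4.1.3:

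- Add to every hypoglycaemia summary, including those in 6.3.1.5, the number of episodes per 1000 years of exposure in that arm and period, as for adverse events.
- Name the 0-16 week double-blind summary as the placebo comparison. Use the same event window in both arms, or compare by rates. If the placebo window is cut at week 16, start its open-label window there too, so that no episode falls between the two.
- Footnote the on-treatment table: counts and percentages cover 52 v 16 weeks (plus the tail) and are not directly comparable between arms.

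The cost is about one column, using exposure already needed for the adverse-event rates. There are two downsides. With few episodes the rates will be imprecise: at 0.1 per year only about 3.9 and 0.7 episodes are expected. A rate also removes the effect of unequal time only if risk is constant, which is doubtful when dose escalation fills the first 4 to 8 weeks. For that reason the rate should accompany, not replace, the matched 0-16 week comparison.

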### **Anti-liraglutide antibodies**

Anti-liraglutide antibodies will be summarised in terms of the number and percentage of subjects at each visit that are antibody-positive and antibody-negative. Similarly, subjects with cross-reactivity against endogenous GLP-1 and in vitro neutralising effect will be summarised.

In addition, a comparison of the change in HbA1c and body weight between antibody-positive and antibody-negative subjects will be performed using descriptive statistics and graphs. Listings with the individual antibody results will also contain information about the HbA1c levels and body weight measurements. The impact of anti-liraglutide antibodies on safety will be similarly assessed by descriptive comparisons between antibody-positive and antibody-negative subjects.

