**Novo Nordisk**

## 5.2 Rationale for trial design

This trial is designed in accordance with regulatory requirements (FDA 21 CFR 314.126) and recommendations from the literature.

The design has been chosen in accordance with the trial objectives and with input from the Paediatric Committee (PDCO) of the European Medicines Agency's (EMA).

The co-primary efficacy endpoints are change in BMI SDS from baseline to 16 weeks and 52 weeks. Change in BMI SDS is selected based on the EMA recommendation regarding the assessment of efficacy of new medicinal products for the treatment of obesity in children. The first 16 weeks will be placebo-controlled and double-blinded to evaluate the effect of liraglutide versus placebo, as an adjunct to a structured program for diet and physical activity. The 36-week open-label period will provide supportive evidence to evaluate the continued efficacy and safety of liraglutide. Placebo injections will be stopped at the end of the double-blind period to avoid inconvenience to the subjects.

The rationale for choosing a treatment duration of 16 weeks for the primary efficacy endpoint is that this time period is considered adequate to show effect of liraglutide treatments on the endpoint, and to minimise the duration of placebo injections. The 36-week open-label period will allow additional time to evaluate the full effect of liraglutide on other efficacy endpoints including BMI, body weight, waist to hip circumference, cardiovascular risk factors (hsCRP and lipid profile), blood pressure and glucose metabolism and safety assessments. Furthermore, a 52-week total trial period is regarded to be sufficient to characterise the safety and tolerability profiles of liraglutide.

A 2:1 randomisation was chosen to ensure more subjects will receive active treatment with limited number of subjects enrolled in the trial, and therefore more safety data on liraglutide treatment is obtained.

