#### 5.3.1.2 Dose escalation part B

Based on result of the safety and PK data of NN8022-4181 and part A of NN8022-4179, the recommendation for part B - PWS children (aged 6 to < 12 years) with obesity is to initiate treatment with liraglutide/placebo based on weight.

Protocol: Liraglutide  
Trial ID: NN8022-4179  
UTN: U1111-1162-7884  
EudraCT no.: 2014-004415-37

CONFIDENTIAL

Date: 16 July 2020  
Version: 5.0  
Status: Final  
Page: 33 of 125

Novo Nordisk

For children with a body weight  $\geq 45$  kg, dosing will be initiated with liraglutide/placebo 0.6 mg daily for one week and increased in weekly steps of 0.6 mg until a maximum tolerated dose (MTD) (as judged by the investigator) or a dose of 3.0 mg liraglutide/placebo is reached.

For children with a body weight  $< 45$  kg, dosing will be initiated with liraglutide/placebo 0.3 mg daily for one week and increased to 0.6 mg after the first week, thereafter the dose is increased in weekly steps of 0.6 mg until a MTD (as judged by the investigator) or a dose of 2.4 mg liraglutide/placebo is reached.

Escalation of the liraglutide/placebo dose is not allowed if the subject has a SMBG  $< 3.1$  mmol/L (56 mg/dL) or  $< 3.9$  mmol/L (70 mg/dL) in the presence of symptoms of hypoglycaemia during the week prior to the dose escalation visits.

Hypoglycaemic episodes must be reported according to Section [8.5.2](#).

Dose escalation will be based on tolerability as assessed by the investigator. The trial product dose will be escalated only if the current dose is tolerated. If a subject has tolerability issues with the higher dose level (as judged by the investigator), it is allowed to lower to the previous dose level.

If a trial product dose is poorly tolerated during the dose escalation period, subjects are allowed to remain at a dose level for an additional week, i.e. four times in total, thus the dose escalation will last for eight weeks in total as a maximum.

Visits and phone contacts to the clinic occur weekly during dose escalation.

Trial Product dose at V8 will be defined as MTD.

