### **8.5.8 Anti-liraglutide antibodies**

Blood samples for determination of anti-liraglutide antibodies are collected from all subjects at randomisation (V3) and at the end of the 16-week double-blind period, see section [2](#). Only samples from subjects treated with liraglutide are analysed for anti-liraglutide antibody development. Depending on the number of subjects in the liraglutide treatment arm, baseline (randomisation V3) from subjects in the placebo group may be analysed for the purpose of determination of the assay cut points. At V19 and V20 antibody samples are collected and analysed from subjects treated with liraglutide only.

Blood samples for the determination of anti-liraglutide antibody must be drawn in a fasting state and prior to administering trial product (see section [2](#)). The anti-liraglutide antibody sample at V20 is to be taken minimum 2 hours after the last meal.

Samples are analysed by the special laboratory for anti-liraglutide antibody formation including cross reactivity to endogenous GLP-1. Furthermore samples from the follow up visit (V20) that are found to be positive for anti-liraglutide antibodies will be analysed for neutralising effect against liraglutide. Anti-liraglutide antibody positive samples from V20 that are also found to cross react with endogenous GLP-1 will in addition be analysed for neutralising effect against endogenous GLP-1. The neutralising antibody analyses will be performed by Novo Nordisk A/S. Baseline antibody samples collected at the randomisation visit will be included in the neutralising antibody analyses for assessment of assay cut points. See further information in sections [8.2](#) and [24.2](#).

Protocol: Liraglutide  
Trial ID: NN8022-4179  
UTN: U1111-1162-7884  
EudraCT no.: 2014-004415-37

~~CONFIDENTIAL~~

Date: 16 July 2020  
Version: 5.0  
Status: Final  
Page: 58 of 125

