### Anti-liraglutide antibodies

Anti-liraglutide antibodies will be summarised in terms of the number and percentage of subjects at each visit that are antibody-positive and antibody-negative. Similarly, subjects with cross-reactivity against endogenous GLP-1 and in vitro neutralising effect will be summarised.

In addition, a comparison of the change in HbA1c and body weight between antibody-positive and antibody-negative subjects will be performed using descriptive statistics and graphs. Listings with the individual antibody results will also contain information about the HbA1c levels and body weight measurements. The impact of anti-liraglutide antibodies on safety will be similarly assessed by descriptive comparisons between antibody-positive and antibody-negative subjects.

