## 5 Statistical analyses

### 5.1 General considerations

Results from the statistical analysis will generally be presented by two-sided confidence intervals (CIs) with a confidence level of 95%. Superiority will be claimed if the two-sided p-value is less than 5% and the treatment estimate favours liraglutide. If the upper limit is below 0, superiority of liraglutide against placebo can be concluded.

The full analysis set (FAS) will be used in the analysis of the efficacy endpoints. For the safety endpoints, the safety analysis set (SAS) will be used. The definition of the analysis sets is given in Section [4](#).

The baseline value will be defined as the last measured and available value from V3 (randomisation) and V2 (screening). Laboratory and PK values below the lower limit of quantification (LLOQ) will be set to  $\frac{1}{2}$ LLOQ.

All analysis will be performed for part A , part B and all subject (which includes both part A and B).

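### The antibody-positive versus antibody-negative comparison tracks adiposity only by body weight, which is not adjusted for growth; BMI SDS and age by antibody status should be added.

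*SAP*

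**What the plan says.** SAP 5.4.1.3 (Anti-liraglutide antibodies) first counts antibody-positive and antibody-negative subjects by visit, with cross-reactivity to endogenous GLP-1 and in vitro neutralising effect. It continues: "In addition, a comparison of the change in HbA 1c and body weight". The contrast in "body weight between antibody-positive and antibody-negative subjects will be performed using descriptive statistics and graphs" names no model and no covariate. The individual listings carry the same two variables. Protocol 17.4.1.2 has the same plan and adds a safety counterpart: "The impact of anti-liraglutide antibodies on safety will be similarly assessed by descriptive comparisons between antibody-positive and antibody-negative subjects".

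Three other places bear on it:

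- Protocol 8.5.8: "Only samples from subjects treated with liraglutide are analysed for anti-liraglutide antibody development". The groups are therefore formed within the active arm, by something observed after randomisation.
- SAP 5.1: "All analysis will be performed for part A , part B and all subject". Part A is 12 to under 18 years and part B is 6 to under 12.
- Protocol 4.2.1 and SAP 6.3.1.1: BMI SDS, referenced to age and sex through WHO data, is the co-primary scale and is derived for baseline, week 16 and week 52.

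**The concern.** A child who keeps the same relative BMI still gains weight while growing, and the amount depends on age. The sponsor expects growth, since the SAP adds height velocity as a safety endpoint. If antibody-positive subjects happen to be younger than antibody-negative ones, they will tend to show a poorer percentage weight response for that reason alone. If they are older, some real loss of effect could be hidden. If ages balance, growth still widens the spread in both groups and makes a small contrast harder to read. BMI SDS takes out most of this and already exists in the data, but it is not among the variables compared. What is at stake is how clearly one can read the adiposity side of the immunogenicity assessment.

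**Working it through.** **The plan's own figure.** None is attached to the antibody comparison. The only yardstick is the planning effect in protocol 17.1: a BMI SDS difference of 0.23, described as about 5-6% of BMI, for week 16. It reproduces. The corrected difference is 0.9 × 0.23 = 0.207 and the corrected SD is √(0.25² + ⅔ × 0.1 × 0.9 × 0.23²) = 0.256. At 2:1 and two-sided 5%, 19 + 38 = 57 subjects give 80.6% power (noncentral t). This confirms the yardstick and has no other bearing here.

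**Growth with no change in relative BMI.** One-year weight ratio = (BMI at age t+1 ÷ BMI at age t) × ((h + g) ÷ h)². BMI is the girls' 95th percentile in Appendix A, Table 3. Height h and gain g are assumptions.

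| Age | BMI, kg/m² | h, g (cm) | Ratio | Weight gain |
|---|---|---|---|---|
| 8 to 9 | 19.4 to 20.2 | 125, 5 to 6 | 1.126 to 1.144 | 13-14% |
| 12 to 13 | 23.3 to 24.4 | 148, 4 to 6 | 1.105 to 1.134 | 10-13% |
| 17 to 18 | 27.4 to 27.7 | 160, 0 to 0.5 | 1.011 to 1.017 | 1-2% |

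**Slope within part A.** The gap between ages 12 and 17 is 10.5 − 1.7 = 8.8 to 13.4 − 1.1 = 12.3 points. Over 5 years that is 1.8 to 2.5, say 2 points per year of age, at week 52. If growth is linear in time, week 16 gives 2 × 16/52 = 0.6.

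**Wider assumptions.** These use boys on the Appendix A, Table 1 cut-off.
- Age 13 (26.84 to 27.63; 148 cm, +2 to +7 cm) gives 5.7-12.9%, with 8.6% at +4 cm.
- Age 17 (29.41 to 30; 155 cm, 0 to +1 cm) gives 2.0-3.3%, with 2.7% at +0.5 cm.
- The central slope is (8.6 − 2.7)/4 = 1.5 points per year. The extremes are (5.7 − 3.3)/4 = 0.6 and (12.9 − 2.0)/4 = 2.7.

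**Part B.** On the same cut-off with +5 cm, age 7 (120 cm) gives 13.6% or 4.0 kg, and age 11 (140 cm) gives 11.2% or 5.5 kg. The gap is 2.4 points over 4 years, or 0.6 per year. In kg it runs the other way.

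**All subjects.** Age 9 (130 cm, +5 cm) gives 13.7% and age 15 (153 cm, +1 cm) gives 3.4%, a gap of 10.3 points at week 52. The artefact is this gap times the difference in the share of children between antibody groups. Differences of 10, 30 and 50 percentage points give about 1, 3 and 5 points of weight.

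**Chance imbalance.** Protocol Table 17-2 plans 22 liraglutide subjects in part A. Assume ages uniform over 12 to 18, so the SD is 6/√12 = 1.73 years, and assume 5 of 22 are positive. The SD of the difference in mean age is 1.73 × √(1/5 + 1/17) = 0.88 years. At 2 points per year this is 1.8 points at week 52 and 0.5 at week 16. Slopes of 0.6 to 2.7 give 0.5 to 2.4 at week 52. With 2 positive the age SD is 1.28 years, and with 11 it is 0.74. No systematic link between age and antibodies is needed.

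**The case against.** A reader might infer that the weight comparison mainly reflects age. The documents do not support that. Bias needs an age difference between antibody groups, and no ages by antibody status are given. In the pooled contrast, growth reaches 5 points at week 52 only with about a 50-point imbalance in the share of children. It is also tempting to set a one-year growth gap of 9-12 points against the 5-6% effect, but that effect belongs to week 16. Protocol 17.1 says only that the 52-week effect should be considerably larger. On the week-16 scale even the 12-versus-17 extreme is 8.8 × 16/52 = 2.7 to 12.3 × 16/52 = 3.8 points, below 5-6%.

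Nor is weight the only look at whether antibodies affect response. HbA1c sits in the same sentence and does not share this growth artefact, and neutralising effect, cross-reactivity and individual listings are planned too. Protocol 5.2 does not say that BMI SDS was chosen to remove growth; it says "Change in BMI SDS is selected based on the EMA recommendation regarding the assessment of efficacy". Analysis by part already removes the child-versus-adolescent contrast. The text does not say whether weight change is in kg or percent, and output detail is left to a programming specification. The height gains are assumptions in a population with short stature, some of it on growth hormone.

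All of that stands and limits the point. It does not answer the remaining gap: the sole adiposity measure is not growth-adjusted, part A spans six years, and the groups will be small.

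BMI SDS is not a perfect remedy. It does not make the groups randomised, and above 3 SD one unit corresponds to an age-specific BMI interval (SAP 6.3.1.1). That is a reason to add it rather than to substitute it for weight, which the protocol names.

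**Conclusion.** The point holds as a minor improvement. The weight contrast between antibody groups can be confounded or blurred by age, and by-part results reduce this without removing it, chiefly in part A. The size is roughly 2 percentage points of weight at week 52 (0.6 to 2.7 over the assumptions tried) and about 0.6 at week 16 per year of mean age difference within part A. This rests on assumed heights and height gains, constant relative BMI, and linear growth for the week-16 figure. Whether any bias occurs, and in which direction, cannot be known from the documents. The comparison is descriptive, with no test, decision rule or claim attached, so no sample-size or error-rate figure changes.

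**What to change.** In SAP 5.4.1.3, add change from baseline in BMI SDS at weeks 16 and 52 to the antibody-positive and antibody-negative summaries, graphs and individual listings. Keep body weight and HbA1c as planned. Show the results by part, and report baseline age by antibody status so that a reader can judge any imbalance. Record the addition in SAP Appendix 2, which already lists added BMI SDS (%) and BMI (%) analyses.

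The cost is one extra variable in existing outputs and one age summary. No new data are needed: height and weight are scheduled at baseline, week 16 and week 52, and BMI SDS is derived from them. Because body weight stays, nothing specified in the protocol is dropped.
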